**Exclusion criteria:**

1. Have predominantly pustular, erythrodermic, and/or guttate forms of psoriasis.
2. History of an ongoing, chronic or recurrent infectious disease, or evidence of tuberculosis infection as defined by a positive tuberculin purified protein derivative (PPD) or QuantiFERON TB-Gold test (QFT) at Screening. Subjects with a positive or indeterminate PPD or QFT test may participate in the study if a full tuberculosis work up (according to local practice/guidelines) is completed within 12 weeks prior to randomization and establishes conclusively that the subject has no evidence of active tuberculosis. If presence of latent tuberculosis is established, then treatment must have been initiated at least for 4 weeks prior to randomization and the course of prophylaxis is planned to be completed.
3. Subjects with a history of HIV, or history of positive HCV or HBV
4. Use of any of the following therapies within 4 weeks prior to Baseline (Visit 2): systemic non-biologic psoriasis therapies (including, but not limited to): psoralens and ultraviolet A (PUVA) therapy, cyclosporine, methotrexate, azathioprine, corticosteroids, apremilast, tofacitinib, oral retinoids, mycophenolate mofetil, sirolimus; 1, 25 dihydroxyvitamin D analogs; or phototherapy (including UVB or self-treatment with tanning beds or therapeutic sunbathing) or topical psoriasis therapy with psoralens.
5. Use of topical corticosteroid preparations, topical calcineurin inhibitors, or other topical preparations with immunomodulatory properties within 2 weeks prior to Baseline (Visit 2).

6. Use of any investigational drug or any systemic drug for psoriasis within four weeks prior to Baseline (Visit 2).
7. Serious concomitant illness that could require the use of systemic corticosteroids or otherwise interfere with the patient's participation in the trial.
8. Clinically important deviation as judged by the investigator (such WBC< 3) from normal limits in physical examination, vital sign measurements, clinical laboratory tests results, not associated with a chronic, well-controlled medical condition.
9. Any active live-vaccines 3 months prior to baseline and throughout the study.
10. Have a current or history of lymphoproliferative disease within 5 years prior to Baseline (Visit 2); or have current or history of any malignant disease within 5 years prior to Baseline (Visit 2).
11. History of suicide attempt, or are clinically judged by investigator to be at risk of suicide.
12. History of Crohn's disease.
13. Had a serious infection, been hospitalized, or received IV antibiotics for an infection, within 12 weeks prior to Baseline (Visit 2).
14. Known immunodeficiency, or history of infection typical of an immunocompromised host.
15. At screening, have a neutrophil count <1500 cells/uL.
16. At screening, have a lymphocyte count <800 cells/uL.
17. At screening, have a platelet count <100,000 cells/uL.
18. At screening, have a total white blood count (WBC) < 3000 cells/uL.
19. At screening, have a hemoglobin <8.5 g/dL.
20. Have donated >450 mL of blood within 4 weeks prior to screening (Visit 1), or intend to donate blood during the course of the study.
21. Women who are lactating or breastfeeding.
22. Any other condition that precludes the patient from following and completing the protocol, in the opinion of the investigator.

#### **STATISTICAL METHODS:**

Individual efficacy variables, the sum of those variables, and safety parameters will be analyzed separately. Subjects who discontinue prematurely because of inadequate response or because of adverse events will have their last results carried forward for purposes of analysis.

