## **ENDPOINTS:**

**Primary endpoint:** Proportion of patients achieving a score of “0-clear” or “1-almost clear” in the sPGA score after 16 weeks of treatment.

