### **Secondary endpoints:**

1. Proportion of patients achieving PASI-100 response after 16 weeks of treatment.
2. The proportion of patients who achieve an improvement of 50% or greater in BSA involvement after 16 weeks of treatment.
3. Proportion of patients achieving PASI-75 response after 16 weeks of treatment.
4. Proportion of patients achieving PASI-90 response after 16 weeks of treatment.

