## **RESEARCH DESIGN:**

This is an open-label study of a total of 40 subjects enrolled at 3 to 4 sites, with moderate-to-severe psoriasis who have previously failed treatment with an IL-17A agent. Subjects will receive brodalumab 210 mg via subcutaneous injection at weeks 0, 1, and 2, followed by 210 mg every 2 weeks; total study length is 16 weeks.

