## **METHODS:**

Informed consent will be obtained at the study site at the time of the first consultation for participation in this study.

After providing informed consent, subjects will be assessed for study eligibility at the Screening visit (day -28 to day -1). At the Screening visit the following procedures will be performed:

1. Medical history and concomitant as well as prior medications/treatments will be reviewed
2. Skin examination will be performed (including assessment of PASI, sPGA, and BSA)
3. Approximately 14 cc (approximately 3 teaspoons) of blood will be drawn for a complete blood count (including differential) (not required if subject can provide results from a previous test performed within 4 months of screening visit).
4. Approximately 5 cc (approximately 1 teaspoon) of blood will be drawn for a QuantiFERON TB-Gold test (QFT) assay; or subjects will undergo tuberculin purified protein derivative (PPD) testing (not required if subject can provide results of a negative test performed within 8 months of screening visit).
5. Females of child bearing potential will have 5 cc (approximately 1 teaspoon) of urine collected for a pregnancy test. This test must be negative in order to qualify for the study.

Subjects will be deemed eligible as per inclusion/exclusion criteria. Qualified subjects meeting all the inclusion and exclusion criteria will be start treatment at Day 0/Baseline (within 28 days of signing the consent form). Female subjects of child-bearing potential will have 2 teaspoons of urine collected for a pregnancy test prior to treatment. This test must be negative in order to continue to qualify for the study. Assessments at this Day 0/Baseline visit include skin examination with assessment of PASI, sPGA, and BSA scores.

Subjects will receive brodalumab (210 mg) via subcutaneous injection using prefilled syringes at Weeks 0, 1, 2, and every 2 weeks thereafter through and including Week 16. Patients will be taught how to administer the drug subcutaneously by a study investigator or designated research staff member at the Baseline visit. They will be dispensed a one-month supply of medication at baseline and each subsequent visit for self-administration at home.

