At Weeks 4, 8, 12 and 16 subjects will return for assessment of concomitant medications and adverse events, and skin assessments including PASI, sPGA, BSA scores, and photography of target lesion(s). In addition, females of child-bearing potential will have 2 teaspoons of urine collected for a pregnancy test at each visit.

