### **Inclusion criteria:**

1. Male or female subject at least 18 years of age
2. Subject is able to provide written informed consent and comply with the requirements of this study protocol.
3. Have both a sPGA score of  $\geq 3$  and BSA  $\geq 5\%$  prior to randomization.

4. Subjects who are women of childbearing potential must have a negative urine pregnancy test at screening and must be practicing an adequate, medically acceptable method of birth control for at least 30 days before Day 0 and at least 6 months after the last study drug administration. Acceptable methods of birth control include intrauterine device (IUD); oral, transdermal, implanted or injected hormonal contraceptives (must have been initiated at least 1 month before entering the study); tubal ligation; abstinence and barrier methods with spermicide. Otherwise, if not of childbearing potential, subjects must: have a sterile or vasectomized partner; have had a hysterectomy, a bilateral oophorectomy or be clinically diagnosed infertile; or be in a menopausal state for at least a year.
5. Tuberculin purified protein derivative (PPD) or QuantiFERON TB-Gold test (QFT) negative at the time of screening, or if patient has a history of positive PPD or QuantiFERON, he/she has initiated or completed the appropriate prophylaxis.
6. Subject is judged to be in good general health as determined by the principal investigator based upon the results of medical history and laboratory profile.
7. Subject has previously failed treatment with an IL-17A agent, secukinumab or ixekizumab, (where available, defined as previous treatment with either drug for at least 3 months without achieving PASI-75 response or a 50% loss of original improvement).
8. Last administration of secukinumab or ixekizumab  $\geq$  28 days prior to Baseline.

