#### **ADVERSE EVENTS:**

As of July 19, 2016, the brodalumab safety package across multiple indications included 6243 brodalumab-treated patients. The majority of patients were followed for 1 to 2 years, with 102 having follow up for over 5 years. The safety profile of brodalumab in psoriasis patients include 4464 patients, using integrated safety data from the phase 2 and phase 3 trials, and their open-label extensions. Overall, the safety profile of brodalumab was found to be consistent with other biologic agents targeting the IL-17 pathway.

The most common adverse events ( $\geq 2\%$  of patients) in patients exposed to brodalumab 210 mg q2w were nasopharyngitis, upper respiratory tract infection, arthralgia, and headache. Adverse drug reactions include headache, arthralgia, fatigue, oropharyngeal pain, diarrhea, nausea, myalgia, influenza, injection site reactions, neutropenia, and tinea infections, conjunctivitis, and candida infections.

Through the end of the psoriasis studies, a total of 23 deaths were reported among the patients who received brodalumab. This includes a total of 4 completed suicides, including one reported as an intentional overdose. There was no increase in overall risk of death above what would be expected in the patient population.

There were no differences in the rates of serious adverse events at week 12 of treatment between brodalumab, ustekinumab, or placebo. Overall, the rates of adverse events leading to discontinuation of treatment were low and comparable to placebo at week 12 and ustekinumab at week 52, with no increase through the long term period. Serious adverse events with incidence rates  $\geq 0.1\%$  in the brodalumab patients at week 12 were cellulitis, appendicitis, gastroenteritis, and acute pancreatitis. Major Adverse Cardiovascular Events (MACE) were reported at 0.2% at 12 weeks in brodalumab exposed patients, and 0.61 per 100 patient years in the all-brodalumab group at week 52 as compared to 0.40 in the ustekinumab group. The sponsor concluded that there was no evidence for a causal association between MACE and brodalumab.

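### Carry-forward can count an adverse-event drop-out as a Week-16 responder, and the plan has no rule for other missing Week-16 results and names no analysis set

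*Combined protocol and SAP*

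**What the plan says.** The primary endpoint (Endpoints) is the proportion of patients scoring 0 or 1 "in the sPGA score after 16 weeks of treatment". The four secondary endpoints have the same form, for example "Proportion of patients achieving PASI-75 response after 16 weeks of treatment". Research Design describes the trial: "This is an open-label study of a total of 40 subjects enrolled at 3 to 4 sites".

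Statistical Methods consists of two sentences. The one on missing data reads: "Subjects who discontinue prematurely because of inadequate response or because of adverse events will have their last results carried forward for purposes of analysis". It covers two reasons for stopping and no others. Neither sentence names an analysis set or a denominator, and no other section does.

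On when scores are taken, Methods says: "At Weeks 4, 8, 12 and 16 subjects will return for assessment", which includes the skin scores. Early Termination foresees subjects leaving by choice, by investigator decision and for pregnancy. It asks those who leave by choice or are withdrawn by the investigator to attend a final visit at which some or all of the listed procedures, skin scores among them, are done. Appendix A labels its last column V6/ET, sets it at Week 16, and marks sPGA, PASI and BSA there.

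**The concern.** There are two separate problems.

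The first is the stated rule. A subject could reach sPGA 0 or 1 at Week 4, stop for an adverse event, have no later score, and still count as a success after 16 weeks of treatment. The endpoint wording and the rule point in different directions for that subject.

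The second is what the rule omits. Subjects who leave by choice or for pregnancy, who are lost to follow-up, or who miss the Week-16 visit could be excluded, counted as non-responders, or scored from a final or last available visit. The text does not choose between these. Results are open-label, so the choice could be made after they are known.

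With one arm, the response proportion is the main efficacy result, and no control arm is handled by the same rule. The secondary responder endpoints are affected in the same way.

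**Working it through.** **The plan's own figure.** The only design figure is n = 40. The documents give no error rate, power, reference rate, target rate or expected drop-out, so 40 can be neither reproduced nor refuted. What can be checked is how far the primary proportion moves under the readings the text allows.

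**Inputs from the documents.** n = 40 (Research Design), all assumed to be treated. Inclusion criterion 3, which opens "Have both a sPGA score of", sets the baseline sPGA at 3 or more. A carried-forward baseline score is therefore always a non-response, and only a later 0 or 1 can raise the rate.

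**Assumed inputs.**
- R = 21 completer responders.
- k = adverse-event drop-outs with last sPGA 0 or 1, from 0 to 2.
- m = subjects under no rule, from 0 to 2.
- Drop-outs for inadequate response are taken to have a last sPGA above 1.

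**Formulas.**
- Every drop-out a non-responder: R/40
- Plan, the m subjects as non-responders: (R + k)/40
- Plan, the m subjects excluded: (R + k)/(40 − m)
- Plan, the m subjects scored from a final or last available visit, at most: (R + k + m)/40

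**Main case.** Two adverse-event stops (one of them at 0 or 1), two inadequate-response stops and one stop under no rule leave 40 − 5 = 35 completers, of whom 21 respond. Exact (Clopper-Pearson) 95% intervals:

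| Handling | Rate | 95% interval |
|---|---|---|
| Every drop-out a non-responder | 21/40 = 52.5% | 36.1 to 68.5 |
| Plan, other drop-out a non-responder | 22/40 = 55.0% | 38.5 to 70.7 |
| Plan, other drop-out excluded | 22/39 = 56.4% | 39.6 to 72.2 |
| Plan, other drop-out scored 0 or 1 | 23/40 = 57.5% | 40.9 to 73.0 |

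The stated rule adds 55.0 − 52.5 = 2.5 points. The unstated handling adds 0 to 2.5 more.

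**Range (rates in %).** Counting every drop-out as a non-responder gives 52.5 in each row.

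| k | m | m as non-responders | m excluded | m scored, maximum |
|---|---|---|---|---|
| 0 | 0 | 52.5 | 52.5 | 52.5 |
| 0 | 1 | 52.5 | 53.8 | 55.0 |
| 0 | 2 | 52.5 | 55.3 | 57.5 |
| 1 | 0 | 55.0 | 55.0 | 55.0 |
| 1 | 1 | 55.0 | 56.4 | 57.5 |
| 1 | 2 | 55.0 | 57.9 | 60.0 |
| 2 | 0 | 57.5 | 57.5 | 57.5 |
| 2 | 1 | 57.5 | 59.0 | 60.0 |
| 2 | 2 | 57.5 | 60.5 | 62.5 |

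The rows with m = 0 show a single value: for adverse-event stops alone, the written rule leaves nothing open. The readings diverge only when m > 0.

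**Dependence on R.** The stated rule adds k/40 whatever R is. Scoring the m subjects adds at most m/40. Excluding them adds (R + k)m/[40(40 − m)], which cannot exceed m/40 because R + k is at most 40 − m. The bounds of 5.0 points each (2/40) therefore do not rest on R = 21. The largest rate shown, 62.5%, lies within the 36.1 to 68.5 interval around 21/40.

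**The case against.** Carry-forward is a prespecified convention, and using the last score as the Week-16 value is simply what it does. That stands. A reader might infer that an adverse-event drop-out alone leaves the primary proportion undefined, but the documents do not support this: the rule names that case and gives one number. Investigator withdrawals for compromised safety would mostly be adverse-event stops and so are covered too.

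A reader might also infer that carry-forward overstates the drug's effect. That does not follow. The rule can only equal or exceed non-responder counting, but against the rate had everyone stayed on treatment it could err either way, because an early score may precede full response.

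Nor are the open readings equally likely. The V6/ET column puts an early-termination sPGA, PASI and BSA in the Week-16 slot, which favours scoring from the final visit. It is a schedule of procedures, though, not an analysis rule, and Early Termination requires only some or all of the procedures. Likewise, all 40 subjects is the natural denominator, but it is not written.

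Finally, the effect may be small or nil. The Adverse Events section reports that in earlier trials "the rates of adverse events leading to discontinuation of treatment were low and comparable to placebo at week 12". This tempers the point. It does not remove it, because neither the proportion nor its interval can be computed until numerator and denominator are fixed.

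**Conclusion.** The point holds in two limited parts, and it should be fixed.

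1. The stated rule credits adverse-event drop-outs last seen at sPGA 0 or 1 with a response after 16 weeks that they did not complete. This is worth 2.5 points per subject relative to non-response, and 0 to 5.0 points for up to two such subjects.
2. Subjects missing Week 16 for reasons outside the rule have no stated handling, and the denominator is unstated. This is worth a further 0 to 5.0 points for up to two such subjects.

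The drop-out counts are assumptions. With none of either type, the gap is zero. The shifts stay inside sampling error, and no success threshold exists for them to cross. The harm is an efficacy result that could depend on a choice made after the data are seen; the documents do not show that a wrong conclusion would follow.

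**What to change.** Replace the carry-forward sentence in Statistical Methods with:

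> All subjects who receive at least one dose are in the denominator. For sPGA 0/1, PASI-75/90/100 and BSA-50, any subject who permanently stops study drug or leaves the study before the Week-16 visit, or who has no Week-16 assessment, for any reason, is a non-responder; an early-termination score is not a Week-16 result.

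Naming both stopping the drug and leaving the study matters. Otherwise a subject who stops treatment early but attends Week 16 could still count as a responder.

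Report two sensitivity analyses: carry-forward, including early-termination scores, and observed cases. Any other single prespecified rule covering every reason would also remove the ambiguity in the second part.

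The cost is one paragraph and no new data. The downside is that the reported rate may be slightly lower, and counting all such subjects as non-responders is a conservative convention that can understate response.

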#### **ADVERSE EVENTS:**

As of July 19, 2016, the brodalumab safety package across multiple indications included 6243 brodalumab-treated patients. The majority of patients were followed for 1 to 2 years, with 102 having follow up for over 5 years. The safety profile of brodalumab in psoriasis patients include 4464 patients, using integrated safety data from the phase 2 and phase 3 trials, and their open-label extensions. Overall, the safety profile of brodalumab was found to be consistent with other biologic agents targeting the IL-17 pathway.

The most common adverse events ( $\geq 2\%$  of patients) in patients exposed to brodalumab 210 mg q2w were nasopharyngitis, upper respiratory tract infection, arthralgia, and headache. Adverse drug reactions include headache, arthralgia, fatigue, oropharyngeal pain, diarrhea, nausea, myalgia, influenza, injection site reactions, neutropenia, and tinea infections, conjunctivitis, and candida infections.

Through the end of the psoriasis studies, a total of 23 deaths were reported among the patients who received brodalumab. This includes a total of 4 completed suicides, including one reported as an intentional overdose. There was no increase in overall risk of death above what would be expected in the patient population.

There were no differences in the rates of serious adverse events at week 12 of treatment between brodalumab, ustekinumab, or placebo. Overall, the rates of adverse events leading to discontinuation of treatment were low and comparable to placebo at week 12 and ustekinumab at week 52, with no increase through the long term period. Serious adverse events with incidence rates  $\geq 0.1\%$  in the brodalumab patients at week 12 were cellulitis, appendicitis, gastroenteritis, and acute pancreatitis. Major Adverse Cardiovascular Events (MACE) were reported at 0.2% at 12 weeks in brodalumab exposed patients, and 0.61 per 100 patient years in the all-brodalumab group at week 52 as compared to 0.40 in the ustekinumab group. The sponsor concluded that there was no evidence for a causal association between MACE and brodalumab.

Other identified and potential risks of brodalumab treatment include: worsening of Chron's disease; higher rate of infections with the majority reported as nonserious, mild, and self-limited; neutropenia at a rate of 0.7% in the 12-week trial, with most cases reported as transient and reversible; hypersensitivity at a rate of 1.7% for brodalumab 210 mg q2w; and malignancy, with exposure-adjusted event rates at 52 weeks of 0.3 in the all-brodalumab group as compared to 0.4 in the ustekinumab group, with no increase over long term follow up. [5, 6]

Brodalumab was FDA-approved in February, 2017 with a Risk Evaluation and Mitigation Strategy to ensure that prescribers and patients are aware of the risk of suicidal ideation. Investigators will be REMS certified and Study Subjects will sign the Patient-Prescriber Agreement Form prior to initiating study drug.

## **SAFETY MONITORING**

The study will be conducted in accordance with our department's Standard Operating Procedures, which are based on US FDA Title 21 Code of Federal Regulations and ICH Good Clinical Practice guidelines.

An investigator will review all laboratory results and assess for adverse events. The principal investigator will be informed of all adverse events. In the event that a subject's safety is compromised, the investigator will discontinue the subject immediately.

A DSMB will be formed and will be comprised of two board certified dermatologists experienced in prescribing biologic treatments. All SAEs will be reported to the DSMB board within 24 hours of our being informed of the event. In addition, the DSMB will receive a compiled list of all related adverse events, from all sites, every three months, so that they can determine if the risks have changed and whether or not the study should continue as planned.

**Definition of an AE:** Any untoward medical occurrence in a subject administered a pharmaceutical product that does not necessarily have a causal relationship with the treatment. An AE can therefore be any unfavorable and unintended sign (including an abnormal laboratory finding), symptom, or disease temporally associated with the use of a medicinal (investigational) product, whether or not considered related to the investigational medicinal product.

Investigational Medicinal Product (IMP) includes the drug under evaluation and the comparator drug(s) if specified as part of the research objective, given at any time during the study. Medical conditions/diseases present before starting the drug of interest are only considered adverse events if they worsen after starting the drug of interest.

The occurrence of adverse events will be sought by non-directive questioning of the patient at each visit during the study. Adverse events also may be detected when they are volunteered by the patient during or between visits or through physical examination, laboratory test, or other assessments. All adverse events will be recorded in the study database including the following information:

1. the severity grade (mild, moderate, severe)
2. its relationship to the drug(s) of interest (suspected/not suspected)
3. its duration (start and end dates or if continuing at final exam)
4. whether it constitutes a serious adverse event (SAE)

A SAE is any untoward medical occurrence that at any dose:

- results in death,
- is life-threatening,
- requires inpatient hospitalization or prolongation of existing hospitalization,
- results in persistent or significant disability/incapacity,
- is a congenital anomaly/birth defect,
- is otherwise a significant medical event.

This includes any SAEs likely to arise from the trial indication or progression of underlying/concomitant illness (es) (e.g. progression of cancer in oncology trials), unless specified in the protocol as study specific exemptions.

Any SAE, irrespective of causality, occurring after the subject has provided informed consent and until four weeks after the subject has stopped study participation must be reported unless otherwise stated in the protocol. SAEs occurring after four weeks from ending study participation should only be reported if considered by the Investigator

attributable to the exposure to the investigational drug(s) during the trial period. This includes the period in which the study protocol interferes with the standard medical treatment given to a subject, even if study treatment has not yet started (e.g. withdrawal of previous treatment during washout period, change in treatment to a fixed dose of concomitant medication).

**Timelines:** All serious adverse events (SAEs) from interventional clinical trials must be reported by the sites to the Lead PI within 24 hours of occurrence of the SAE and to the site's own IRB as required. The Lead PI will then report to the manufacturer and any other authorities.

**Follow-up reports:** All related SAEs will be followed until resolution or until it is judged to be permanent, and an assessment will be made at each visit (or more frequently, if necessary) of any changes in severity, the suspected relationship to the drug of interest, the interventions required to treat it, and the outcome.

**Pregnancies:** Any occurrences of a pregnancy in a patient (or a patient's partner) during study participation will be collected. All pregnancies will be followed up to determine outcome, including spontaneous or voluntary termination, details of the birth, and the presence or absence of any birth defects, congenital abnormalities, or maternal and/or newborn complications.

Should a temporary or permanent suspension occur, we would report the occurrence to all appropriate authorities.

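### Low-cost improvement: the DSMB's three-monthly list covers only related adverse events, so non-serious events marked not suspected have no stated route to the board

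*Combined protocol and SAP*

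**What the plan says.** Safety Monitoring sets up a DSMB of two dermatologists and gives it two streams of information.

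- **Serious events:** "All SAEs will be reported to the DSMB board within 24 hours of our being informed of the event". This stream has no causality filter.
- **Periodic list:** "the DSMB will receive a compiled list of all related adverse events, from all sites, every three months". Its purpose follows in the same sentence: "so that they can determine if the risks have changed and whether or not the study should continue as planned".

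The same section describes what is collected: "All adverse events will be recorded in the study database including the following information". The items are severity grade, causality, duration and seriousness. Causality is a two-way call: "its relationship to the drug(s) of interest (suspected/not suspected)". The section also says that the principal investigator is informed of every adverse event.

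Research Design describes an open-label study of 40 subjects at 3 to 4 sites, all given brodalumab. Safety is the secondary objective.

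**The concern.** The periodic list is the DSMB's only stated regular view of non-serious events, and it is filtered by investigator causality before the board sees it. That sits badly with the list's purpose. A change in risk can appear as an accumulation of events, each of which looks unremarkable to the investigator who sees it. Someone has to view all the events together to notice this.

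The design makes the filter matter more. Treatment is open-label and no control arm is described. (The eligibility criteria and the schedule mention randomization, but only one treatment is described.) The causality call is therefore made event by event, by people who know that the subject is on brodalumab, with no concurrent group against which to check it. If the calls at the 3 to 4 sites lean towards not suspected, the board's list shortens and nothing on the list shows that this has happened.

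What is at stake is the quality of safety oversight during the study. The estimation of efficacy is not involved.

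**Working it through.** The plan gives no figure to reproduce, and no sample size, error rate or event count enters the point. The check is to trace each class of adverse event to its stated route to the DSMB. All routes come from Safety Monitoring.

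| Class of event | 24-hour report to DSMB | Three-monthly list | Recorded in database |
|---|---|---|---|
| Serious, suspected | yes | yes | yes |
| Serious, not suspected | yes | no | yes |
| Non-serious, suspected | no | yes | yes |
| Non-serious, not suspected | no | no | yes |

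Step by step:

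1. **Serious events.** The 24-hour rule covers all of them. The SAE reporting paragraph separately says that causality is irrelevant to whether an SAE is reported. Both serious rows reach the board.
2. **Non-serious, suspected.** These reach the board through the list, provided that related means suspected. The protocol does not define related. Equating it with the recorded suspected category is an inference, though the natural one, since that is the only causality field collected.
3. **Non-serious, not suspected.** These reach the database and the principal investigator. No sentence sends them to the DSMB. This is the only row with no stated route to the board.
4. **Size of that row.** The documents give no split between suspected and not suspected events, and no expected number of events for this study. The omitted share cannot be calculated, and none is assumed here.
5. **Whether the data for a fuller list exist.** Severity, causality and seriousness are already recorded for every adverse event, so an unfiltered list can be drawn from the existing database.
6. **What an unfiltered list still lacks.** A list of events without a denominator cannot show a rate. As an illustration, one affected subject is 1/40 = 2.5% of the planned total, but 1/15 = 6.7% if only 15 subjects (the drug supply for one site) have been treated. The number treated to date has to be on the list.

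**The case against.** The strongest reply is that this is a choice about the length of one list, and that the safeguards around it are substantial. No passage contradicts another. The SAE definition includes a criterion for any otherwise significant medical event, so an event judged medically significant goes to the board within 24 hours whatever its causality. The principal investigator hears of every event, although the text does not say whether this means the site or the lead investigator. Nothing stops the DSMB from asking for more. What is left out has been judged both not serious and not suspected. A longer list would still have no comparator.

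Most of this stands, and it limits the point to one class of event. It does not close the gap. The board is the body asked to decide whether the study continues, and it is poorly placed to ask about a pattern that it has not been shown. The missing comparator is a reason to add the number of subjects treated. It is no reason to keep the filter.

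A reader might infer more than the documents support:

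- **That unrelated SAEs are hidden from the DSMB.** They are not. The 24-hour rule covers all SAEs.
- **That particular common events would be filtered out.** Adverse Events says that the most common events "were nasopharyngitis, upper respiratory tract infection, arthralgia, and headache", and the two infections there are not in the list of drug reactions. That list reads: "Adverse drug reactions include headache, arthralgia, fatigue, oropharyngeal pain, diarrhea, nausea, myalgia, influenza, injection site reactions, neutropenia, and tinea infections, conjunctivitis, and candida infections". It is introduced as what the reactions include, so absence from it is weak evidence, and it names several infections. The protocol also names a higher rate of infections among identified and potential risks, which gives an investigator reason to mark one as suspected. Causality is judged per event, so the comparison does not show what the filter would remove.
- **That the rule on following related SAEs to outcome is part of the same defect.** It is a separate and narrower matter. Every adverse event has its duration recorded ("start and end dates or if continuing at final exam"), and pregnancy outcomes, including birth defects, are followed whatever the causality. Widening that rule would add an amount of follow-up that the documents do not allow one to estimate. No change to it is proposed here.

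**Conclusion.** The point holds as a low-cost improvement to safety oversight. The protocol states a rule that limits the periodic DSMB list to related events. Under that rule, one class of event out of the four in the table, non-serious and not suspected, has no stated route to the board. The board's periodic review of non-serious events therefore depends on each investigator's causality call, in a study with no control arm described.

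The conclusion rests on reading related as suspected, and on the protocol's wording alone. The department's SOPs, to which Safety Monitoring refers, are not available and could provide for more.

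The size cannot be put in numbers. The documents do not support a claim that many events would be omitted, that any harm would be missed, or that the final safety data would be incomplete. All adverse events are recorded, and neither the efficacy results nor the final safety dataset is affected.

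**What to change.** Reword the one sentence in Safety Monitoring that defines the three-monthly list. Remove the restriction to related events, so that the board receives all adverse events from all sites, showing severity, seriousness and investigator causality for each, together with the number of subjects treated to date. The board can then sort or filter by causality itself.

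The cost is a longer list for two reviewers to read every three months. The documents do not allow its length to be estimated. No new data are collected, because the event-level items are already in the database and the count of treated subjects follows from the drug accountability that each site keeps. The 24-hour SAE route stays as it is.
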